Appendix F. International Prognostic Scoring System (IPSS) for MDS

Scores for risk groups are as follows: Low, 0; INT-1, 0.5-1.0; INT-2, 1.5-2.0; and High, \geq 2.5.

* Good, normal, -Y, del(5q), del(20q); Poor, complex (\geq 3 abnormalities) or chromosome 7 anomalies; Intermediate, other abnormalities.

(Greenberg et al, 1997, page 2085)

AMGEN[®]

Source Data	Information from an original record or certified copy of the original record containing patient information for use in clinical research. The information may include, but is not limited to, clinical findings, observations, or other activities in a clinical trial necessary for the reconstruction and evaluation of the trial. Source data are contained in source documents (original records or certified copies). [ICH Guideline (E6)].
Study day 1	The first day that protocol specified IP is administered to the subject; Day 1 t is expected to align with the end of the active treatment period visit of the MDS 20090160 study (window +10 days)
TIA	Transient ischemic attack
TVE	Thrombovascular event
µg	Microgram
VTE	Venous thromboembolic event
WHO	World Health Organization

1. INTRODUCTION

This statistical analysis plan (SAP) outlines the statistical analyses to be performed for Amgen protocol 20130113 entitled A Single Arm, Companion Study to Myelodysplastic Syndrome (MDS) 20090160 Using Darbepoetin alfa for the Treatment of Anaemic Subjects With Myelodysplastic Syndrome. The analyses summarized here are beyond the analyses described within the SAP version 3.0, dated on 30 September 2013 for data collected within the scope of Amgen protocol 20090160 entitled A Multicenter, Randomised, Double-blind, Placebo-controlled Study of Darbepoetin Alfa for the Treatment of Anaemic Subjects with Low or Intermediate-1 Risk Myelodysplastic Syndromes (MDS). The objective of this SAP is to pre-specify non Clinical Study Report (CSR) -related analyses.

2. OBJECTIVES

The primary objective of this study is to provide required access of investigational product (darbepoetin alfa) beyond the end of active treatment period of the darbepoetin alfa MDS 20090160 study for subjects that have continued demonstration of benefit from darbepoetin alfa treatment and to describe the safety of longer-term use in this patient population. Treatment with darbepoetin alfa may continue for up to 73 weeks or until progression to AML, whichever occurs first.

2.1 Definitions

Progression to Acute Myelogenous Leukemia (AML)

Progression to AML in this study will be assessed according to World Health Organization (WHO) guidelines (peripheral or blast cells \geq 20%, presence of pathognomonic AML cytogenetic change, or evidence of marrow blast criteria for erythroleukemia).

Red Blood Cell (RBC) Transfusions

This is defined as any RBC transfusion (includes packed RBCs or whole blood and excludes platelets) given during an assessment period, regardless of hemoglobin concentration level at the time of transfusion or reason for transfusion. Subjects with at least 1 RBC transfusion during the assessment period will be considered “transfused”. Subjects with no RBC transfusions during the assessment period will be considered “not transfused”.

Treatment-emergent Adverse Event

A treatment-emergent adverse event (AE) is any event reported via the AE summary case report form (CRF) with an onset date between study day 1 and EOS.

- A treatment-emergent serious adverse event (SAE) is any event reported with an onset date between the date the subject signs the Informed Consent Form (ICF) through 30 days after the last dose of IP.
- Day 1 / week 1 dosing visit is expected to align with the end of the active treatment period (EOATP) visit of the MDS 20090160 study (window +10 days)
- End of Study visit performed 3 weeks \pm 7 days after last dose of IP.

Thrombovascular event (TVE)

Thrombovascular events are adverse events that include arterial thromboembolic events (ATEs) and venous thromboembolic events (VTEs). These events will be coded using MedDRA version 17 (or higher) and identified using a Standardized MedDRA Query (SMQ 20000081, “embolic and thrombotic events” excluding terms from the sub-SMQ 20000083, “embolic and thrombotic events, vessel type unspecified and mixed arterial and venous”) or more appropriate query available at the time of analysis. ATEs and VTEs are described below:

- **Arterial thromboembolic event (ATE)**
ATEs include stroke, transient ischemic attack (TIA), acute coronary syndromes (ACS), and other arterial thrombosis/embolism. These events will be coded using MedDRA version 17 (or higher) and identified using the sub-SMQ 20000082 (“embolic and thrombotic events, arterial”) or more appropriate query available at the time of analysis.
- **Venous thromboembolic event (VTE)**
VTEs include deep vein thrombosis (DVT), pulmonary embolism (PE), and other venous thrombosis excluding superficial venous thrombosis. These events will be coded using MedDRA version 17 (or higher) and identified using the sub-SMQ 20000084 (“embolic and thrombotic events, venous”) or more appropriate query available at the time of analysis. In addition, VTEs will be distinguished by whether or not they were confirmed by imaging. The primary analysis of VTEs will include fatal VTEs and VTEs confirmed by imaging; a sensitivity analysis will summarize all VTEs regardless of severity or confirmation.

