6.2.1.1 Dosage, Administration, and Schedule

Darbepoetin alfa will be open-label. The first dose and dosing frequency of darbepoetin alfa on day 1 / week 1 should carry forward from the last dose and frequency from the parent study (darbepoetin alfa MDS 20090160 study) administered at week 70 / 71. The day 1 / week 1 visit should align within +10 days of the EOATP visit at week 72 / 73 from the darbepoetin alfa MDS 20090160 study.

The dosing schedule is described by a schema in the protocol synopsis.

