7. STUDY PROCEDURES

7.1 Schedule of Assessments

| | Screen / Enroll | Active Treatment Period | End of Study ^g |
|--|---------------------------------|---|------------------------------|
| Study Week | 72 / 73 ^a / Day 1 | Q3W or Q2W dosing up to week 73 (Q3W) | 76 |
| Informed Consent | x | | |
| Medical history | x | | |
| Physical examination | x | | |
| Physical measurements (height and weight) ^b | x | performed at each visit | x |
| Vital Signs (heart rate, temperature, blood pressure) | х | performed at each visit | x |
| Assess for signs and symptoms of clinically relevant TVE | x | performed at each visit | x |
| Adverse Events (AEs), Serious Adverse Events (SAEs) ^C | x | performed at each visit | x |
| Key concominant medications, and red blood cell (RBC) transfusions | x | Assessed at each visit and throughout the study | |
| Local laboratory haemoglobin for dosing decision | x | performed at each visit | |
| IP (darbepoetin alfa) administration ^e | х | performed at each visit | |
| Darbepoetin alfa antibody sample collection | x ^f | | х |

Table 5. Schedule of Assessments

a. Last visit of the MDS 20090160 study at week 72 / 73 is the first dosing visit for 20130113.

b. Height only collected as part of screening. Weight collected at each visit.

c. AEs and SAEs will be reported throughout the study through 30 days after last dose of IP (darbepoetin alfa).

d. Dosing will occur Q3W ± 6 day or Q2W ± 6 days. No 2 Q3W or Q2W doses should be administered within any contiguous 14-day or 7-day period, respectively. Dosing decision based on local lab Hb taken within 1 day before IP dosing visit (See Protocol Section 6.2.1.2 for dosing guidelines).

e. Results of local laboratory Hb must be available and reviewed prior to IP adminstration.

f. A Day 1 antibody sample is not required if appropriately collected in the MDS 20090160 study at the End of the Active Treatment Period (EOATP) visit.

g. End of Study (EOS) visit at week 76 or 3 weeks after last dose of IP from Q3W or Q2W dosing for subjects that end IP early.

Page 33

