7.2 General Study Procedures

Refer to the Schedule of Assessments (Table 5) for an outline of the procedures required at each study visit. The investigator at each site is responsible for ensuring that all study procedures are performed as specified in the protocol.

Each subject or their legally authorised representative must personally sign and date the Amgen- / IEC-approved informed consent form (ICF) before any study-specific procedures are performed. The ICF may be reviewed and signed/dated within 8 weeks of the screening assessments.

Demographic data collection including sex, date of birth, age, race, and ethnicity will be collected in order to study their possible association with subject safety data.

Each study visit may occur over a 2 consecutive day period. Study assessments including local laboratory Hb testing may be performed up to 1 day prior to the day of IP administration. For each study visit, all study procedures should be performed prior to IP administration.

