7.2.8 Screening and Enrollment

The following procedures are to be completed during the screening period as noted in the Schedule of Assessments (Table 5):

- Confirmation that the Informed Consent Form has been signed
- Registration in IVR system
- Physical examination
- Physical measurements (height and weight)
- Demographic data including sex, date of birth, race, and ethnicity
- Complete medical history
- Heart rate, temperature, blood pressure
- Adverse event reporting
- Key concomitant medications and RBC transfusion history
- Local laboratory Hb assessment (if applicable)
- IP box number assignment in IVRS (if applicable)
- IP dose administration (if applicable)

Screening assessment, enrollment, and the day of first dose of IP may occur on the same day provided that the subject meets all eligibility criteria prior to IP dosing. The day of first dose may occur up to 10 days after the screening visit to accommodate scheduling. Local laboratory Hb results must be available and reviewed prior to each IP dose administration.

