| □ Scr | eening event (as de | | e protocol) | | | | | | | | | | has ende | d |
| | This is a new even This is follow-up in | | for a previously | OR | | | ibject's a new e | | | | ate in S | Section 2) | | |
| | reported event | | | | | | | | | | r a pre | viously re | ported ev | ent |
| | omplete ALL section on and date the sign | | | the form | | | | | | | | | | |
| | ax completed form (| | | | | er abov | /e Sect | ion 1 | | | | | | |
| | < <for complet<="" td="">ion by A	mgen prior te	o prov	iding to	site	s: SE	LEC	t or	? TY	'PE IN	I A FA)	(#>>		</for> | ion by A | mgen prior te | o prov | iding to | site | s: SE | LEC | t or | ? T Y | 'PE IN | I A FA) | (#>> | |
| 1. SITE IN Site Nun | FORMATION | | Investigator | | | | | | | | Country | , | | |
| Site Null | | | - | | | | | | | | , | | | |
| | Reporter | | Ph | one Numbe | er) | | | | Fa | x Num | ber) | | | |
| 2 SUD IE | CT INFORMATION | | | | / | | | | | | / | | | |
| 2. 30050 | Subject ID Number | | te of Birth | | | Se | ex | | Race | | | | vide End of S | tudy |
| | | | Day Mor | nth Y | ear | | □F □ | м | | | date | | | |
| | bllow-up to an event re te: Day Month _ | | | , Rave), | provide th | e adver | se event | term: | | | | | | _ |
| | JS ADVERSE EVE | | (11.0.1.4 | | | | | | | | | | | |
| | date the Investigator rese Event Diagnosis or | | re of this Serious A | dverse Ev | vent Inforn | Check | Day Enter | Mor Relati | nth onship | Yea | r Relatio | nship | Outcome | Check only |
| When Final E | is unknown, enter Signs liagnosis is known, enter Event per line. If event is fatal, er Entry of "Death" is not acc | Date Started | Date Started Date | | only if event occurred before first dose of IP | Serious Criteria code (see codes | reaso poss that th may ha caus | ere a mable ibility e event ve been ed by 22 | re a Is there a r hable possibility th bility may have bee event an Amger e been | | at the event an caused by | of Event Resolved Not resolved Fatal Unknown | if event is related to study procedure eg, biopsy | |
| | as this is an outcome. | | Day Month Year | Day Mo | onth Year | | below) | Nov | Yee√ | Nov | Yee | fyee, what | - | |
| | | | | | | | | | | | | device? | | |
| | | | | | | | | | | | | | | |
| | | | | | | | | | | | | | | |

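### SAP 2.1 labels as treatment-emergent some events that start before this study's first dose: AEs beginning on day 1 before the injection, and SAEs from consent onward

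*SAP*

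**What the plan says.** SAP 2.1 has two rules.

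- **AEs.** An AE is treatment-emergent if it is "reported via the AE summary case report form (CRF) with an onset date between study day 1 and EOS". The SAP glossary defines study day 1 as "The first day that protocol specified IP is administered to the subject", which is a calendar day and not the moment of injection.
- **SAEs.** An SAE is treatment-emergent if its onset lies between consent signature and 30 days after the last dose.

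The protocol fixes the order of events around the first dose.

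- Protocol 7.2: "For each study visit, all study procedures should be performed prior to IP administration". It adds: "Study assessments including local laboratory Hb testing may be performed up to 1 day prior to the day of IP administration".
- Table 5, footnote a: "Last visit of the MDS 20090160 study at week 72 / 73 is the first dosing visit for 20130113".
- Protocol 6.2.1.1: "The day 1 / week 1 visit should align within +10 days of the EOATP visit at week 72 / 73". Protocol 7.2.8: "The day of first dose may occur up to 10 days after the screening visit to accommodate scheduling".
- Protocol 9.2.1 asks for dates of onset and resolution of each AE. It lists no clock time.

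The sample SAE form in Protocol Appendix B has a box to be checked "only if event occurred before first dose of IP". The SAP does not refer to it.

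The incidence of treatment-emergent AEs is the only endpoint named in Protocol 10.1.1 and SAP 4.1.1. SAP 4.1.2 projects fewer than 10 subjects and replaces summary statistics with listings.

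**The concern.** The label treatment-emergent should mean that an event began once this study's treatment had begun. Neither rule in SAP 2.1 requires that. The AE rule takes in the hours of day 1 before the injection, when the visit assessments are scheduled. The SAE rule takes in the whole interval from consent to first dose. That interval is a sensible window for reporting SAEs to the sponsor, but it does not show that an event emerged on treatment.

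Two features make the boundary worth stating. The day-1 visit is planned to coincide with the last visit of 20090160, so it is where exposure in one study ends and exposure in the other begins. And only onset dates are listed for recording, so if no indicator is captured, the order of event and dose on day 1 may not be recoverable later.

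At stake is whether the listings for the only endpoint contain events that belong before this study's treatment. The protocol draws this line elsewhere: its glossary takes baseline haemoglobin from day 1 before IP is given. The same pre-dose hours are thus baseline for haemoglobin and treatment-emergent for AEs.

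**Working it through.** The plan gives no figure on this point to reproduce, so the check applies the two SAP 2.1 rules to each type of event near the first dose.

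| Event | AE rule (onset date from day 1) | SAE rule (onset from consent) |
|---|---|---|
| Began before day 1, found at the day-1 check | Not counted | Counted if serious and onset is on or after consent |
| Parent-study AE carried forward with its original onset date before day 1 | Not counted | Counted only if serious and onset is on or after consent |
| Found at an assessment the day before dosing, dated that day | Not counted | Counted if serious and consent was already signed |
| Began on day 1 before the injection | **Counted** | **Counted if serious** |
| Began on day 1 after the injection | Counted, correctly | Counted if serious, correctly |

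The second row assumes that carry-forward keeps the original onset date; the protocol does not say so.

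Two results follow.

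1. Through the AE rule, only events that start in the pre-dose hours of day 1 are mislabelled. Through the SAE rule, every SAE that starts between consent and first dose is.
2. The two rules can disagree about one event. An SAE with onset after consent but before day 1 is a treatment-emergent SAE without being a treatment-emergent AE.

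**Reach of the AE rule.** EOS is at week 76, which begins on day 75 × 7 + 1 = 526. Day 1 is 1/526 = 0.19% of the planned days, and only its pre-dose hours are in question.

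**Reach of the SAE rule.** Protocol 7.2 allows consent within 8 weeks of the screening assessments, and Protocol 7.2.8 allows the first dose up to 10 days after the screening visit. The longest gap is 8 × 7 + 10 = 66 days. This assumes consent at the earliest permitted date and use of the full scheduling window. If consent, screening and first dose fall on one day, the gap shrinks to the pre-dose hours of that day.

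The documents give no rate of pre-dose events, so no expected number can be derived from them.

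**The case against.** The strongest defence has four parts.

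- **Subjects are already treated.** They continue the parent study's last dose and frequency, so a pre-dose event on day 1 is not an event in an untreated baseline. This stands and limits the harm to interpretation. It does not make the label right, because events still have to be assigned to one study's treatment or the other's.
- **Counting by date is a cautious convention.** Where only dates are recorded, including all of day 1 avoids losing true post-dose events, and it matches the start of AE reporting in Protocol 7.2.7 and 9.2.1. This stands as a default for events of unknown timing, and the fix keeps it. A reporting window is still not a definition of treatment-emergent, and the argument does not cover the SAE bullet.
- **Nothing is computed.** SAP 4.1.2 plans listings only. This stands. Protocol 10.4 still describes tabulated incidence, but the SAP does not plan it.
- **The box may already exist.** Appendix B is a sample contingency form for use when electronic capture is unavailable, and the AE Summary eCRF is not in the documents. This stands, so the fix is conditional on that point.

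A reader might infer that everything found at the day-1 check enters the endpoint. It does not: the AE rule selects on onset date, so findings with earlier onset, or dated the day before, fall outside it. A reader might also infer that one event is counted twice across the two studies. The documents do not establish this. The shared visit is expected but can be separated by up to 10 days, the data are not to be combined, and the parent study's own AE rule is not available here.

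**Conclusion.** The point holds as a defect of definition with small effect. SAP 2.1 calls two groups of pre-dose events treatment-emergent: AEs that start on day 1 before the injection, and SAEs that start between consent and first dose. The first is a matter of hours on one day. The second can span up to about 66 days on the assumptions stated above.

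Under the SAP no incidence figure changes, and with fewer than 10 subjects very few events are likely to be involved. A percentage-point shift in incidence is a tempting way to size this, but it would describe an output that the SAP does not plan. What remains is that a pre-dose day-1 AE would appear in the treatment-emergent listing that serves the only endpoint, and that pre-dose SAEs carry the same label by explicit rule. This is a desirable clarification and not a threat to the study's conclusions.

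**What to change.** Amend SAP 2.1 as follows.

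1. Define a treatment-emergent AE as one with onset at or after the first 20130113 dose of IP, through EOS.
2. Define a treatment-emergent SAE as one with onset at or after that same dose, through 30 days after the last dose.
3. Keep the interval from consent to first dose as an SAE reporting window only, and list those events separately as pre-dose.
4. For onset dated day 1, use a before-first-dose indicator like the one on the sample SAE form. Add it to the AE Summary eCRF if it is not already there. List flagged events as pre-dose and count unflagged day-1 events as treatment-emergent.

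Items 1 and 2 should be changed together. Changing only the AE rule would leave the SAE bullet in conflict with it.

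The cost is a few SAP sentences, one check box if it is absent, and a separate pre-dose listing. No event is lost from reporting. The remaining weakness is that an unflagged day-1 event still defaults to treatment-emergent, so a missed check box leaves the present behaviour in place for that event.

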3. COVARIATES

No covariates will be used in the analysis of the study.

4. ENDPOINT CATEGORIES AND ANALYSES

4.1 Safety Endpoints

4.1.1 Endpoints

Primary Endpoint: Subject incidence of treatment-emergent adverse events

4.1.2 Analysis Methods

Total enrollment is projected to be less than 10 subjects from 1 country. Given the small population, no summary statistics (descriptive or otherwise) will be provided. Listings will be provided for patient disposition data, baseline demographics, baseline characteristics, IP administration, and important protocol deviations. Listings will also be generated for the primary endpoint of all treatment-emergent adverse events by system organ class and preferred term. In addition, listings will be provided, by system organ class and preferred term, of all fatal adverse events, serious adverse events, adverse events leading to withdrawal from IP and significant treatment emergent adverse events. Progression to AML will also be summarized in a listing.

Listings of subjects who develop anti-darbepoetin alfa antibodies (binding and if positive, neutralizing) at any time will also be provided.

Missing data will not be imputed. Data collected in the study will not be combined with Amgen 20090160 study data.

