4. SUBJECT ELIGIBILITY

Investigators will be expected to maintain a screening log of all potential study candidates that includes limited information about the potential candidate (eg, date of screening). This log may be completed and updated via an Interactive Voice Response (IVR)/Interactive Web Response (IWR) system. Before any study-specific procedure, the appropriate written informed consent must be obtained (see Section 11.1).

| 4.1 | Inclusion Criteria |
|-------|---|
| 4.1.1 | General |
| 101 | Subject or subject's legally acceptable representative has provided informed consent prior to any study-specific activities/procedures being initiated; |
| 102 | Subject must continue LTFU within parent study (20090160); |
| 103 | Subject understands that darbepoetin alfa treatment will not be provided by Amgen past week 73; |
| 104 | Subject completes dosing in the active treatment period (through week 70 or week 71) and completed the end of the active treatment period (EOATP) visit of the parent study (20090160); |
| 4.1.2 | Disease-related |
| 105 | Subject must have an ongoing clinically relevant erythroid response as assessed by the Investigator using current response criteria (ie, IWG response criteria); |

Page 25 of 66

| | Darbepoetin alfa Jumber: 20130113 April 2013 Page 26 of 66 |
|-------|--|
| 4.2 | Exclusion Criteria |
| 4.2.1 | Disease-related |
| 201 | Transfusion dependence defined as receiving a total of ≥ 4 units of RBC transfusion in the previous 8-week period prior to enrolment; |
| 202 | Known diagnosis of acute myelogenous leukemia (AML) or marrow collagen fibrosis; |
| 203 | Known refractory anaemia with excess blast-2 (RAEB-2); |
| 204 | Known diagnosis of intermediate-2 or high risk MDS per IPSS; |
| 4.2.2 | Medications or Other Treatments |
| 205 | Subjects received thrombopoiesis-stimulating factors (eg, eltrombopag, romiplostim) in the MDS 20090160 study or planning to receive such agents during the study; |
| 206 | Subjects receiving any investigational agents/devices not currently approved by the country's regulatory authority for the indication of use. |

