7.3 Antibody Testing Procedures

Blood samples for antibody testing are to be collected on day 1 (prior to darbepoetin alfa dosing) and at the EOS visit for the measurement of anti-darbepoetin alfa binding antibodies. A Day 1 antibody sample is not required if the antibody specimen was appropriately collected in the MDS 20090160 study at the EOATP visit.

Samples testing positive for binding antibodies will also be tested for neutralizing antibodies and may be further characterized for quantity/titer, isotype, affinity and presence of immune complexes. Additional blood samples may be obtained to rule out anti-darbepoetin alfa antibodies during the study.

Sites will be notified of any positive neutralizing antibody results to darbepoetin alfa. If results are not provided, no neutralizing antibodies to darbepoetin alfa have been detected.

Subjects who test positive for neutralizing antibodies to darbepoetin alfa at the final scheduled study visit will be asked to return for additional follow-up testing. This testing

Page 37 of 66

is to occur approximately every 3 months starting from when the site has been notified of the positive result, until: (1) neutralizing antibodies are no longer detectable or (2) the subject has been followed for a period of at least 1 year (± 4 weeks) post administration of darbepoetin alfa. All follow-up results, both positive and negative will be communicated to the sites. More frequent testing (eg, every month) or testing for a longer period of time may be requested in the event of safety-related concerns.

Subjects who test positive for binding, non-neutralizing antibodies and have clinical sequelae that are considered potentially related to an anti-darbepoetin alfa antibody response may also be asked to return for additional follow-up testing.

8. WITHDRAWAL FROM TREATMENT, PROCEDURES, AND STUDY 8.1 Subject's Decision to Withdraw

Subjects have the right to withdraw from the study at any time and for any reason without prejudice to their future medical care by the physician or at the institution.

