10.4 Planned Methods of Analysis

No statistical inferential tests will be done. Incidence of treatment-emergent adverse events will be analyzed using the analysis set. Descriptive summary statistics will be provided for demographic data, cumulative doses, and patient disposition data. Important protocol deviations will be provided. Missing data will not be imputed. Data collected in the study will not be combined with 20090160 study data.

Subject incidence of all treatment emergent adverse events will be tabulated by system organ class and preferred term. Tables of fatal adverse events, serious adverse events, adverse events leading to withdrawal from IP and significant treatment emergent adverse events will also be provided.

The incidence and percentage of subjects who develop anti-darbepoetin alfa antibodies (binding and if positive, neutralizing) at any time will be tabulated.

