5. LIST OF PLANNED TABLES, FIGURES, AND LISTINGS

The following listings will be provided:

- Listing of demographics and baseline characteristics including: enrollment date, sex, age at enrollment, height, weight, heart rate, temperature, blood pressure, and hemoglobin at enrollment
- Listing of treatment emergent adverse events and significant treatment emergent adverse events by system organ class and preferred term
- Listing of fatal adverse events by system organ class and preferred term
- Listing of serious adverse events by system organ class and preferred term
- Listing of adverse events leading to withdrawal from IP by system organ class and preferred term
- Listing of subjects that progressed to AML
- Listing of exposure to IP may include: the number of weeks of dosing, the total number of doses, the average weekly dose ($\mu\text{g}/\text{week}$), the average dose

administered ($\mu\text{g}/\text{dose}$), the cumulative dose administered (μg), the weight-adjusted average dose administered ($\mu\text{g}/\text{kg}/\text{dose}$), and the weight-adjusted cumulative dose administered ($\mu\text{g}/\text{kg}$)

- Listing of Important Protocol Deviations
- Listing of all RBC transfusions given on-study
- Listing of development of anti-darbepoetin alfa antibodies (binding and if positive, neutralizing) at any timepoint
- Listing of Thrombovascular Events including:
 - Arterial thromboembolic events [ATEs]: stroke; transient ischemic attack [TIA]; acute coronary syndromes [ACS]; other arterial thrombosis/embolism;
 - Venous thromboembolic events [VTEs]: deep vein thrombosis [DVT]; pulmonary embolism [PE]; and other venous thrombosis (excluding superficial venous thrombosis).

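### Does the antibody listing need a rule for a subject who is already antibody-positive before the first dose in this study?

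*SAP*

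**What the plan says.** Protocol 7.3 fixes the sampling: "Blood samples for antibody testing are to be collected on day 1 (prior to darbepoetin alfa dosing) and at the EOS visit". The first sample can be waived: "A Day 1 antibody sample is not required if the antibody specimen was appropriately collected in the MDS 20090160 study at the EOATP visit". Table 5, note f, repeats the waiver. A sample positive for binding antibodies is also tested for neutralizing antibodies. The same section allows extra samples during the study. A subject with neutralizing antibodies at the last visit is to be retested about every 3 months until they are no longer detectable or at least 1 year has passed since dosing.

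On reporting, Protocol 10.4 says: "The incidence and percentage of subjects who develop anti-darbepoetin alfa antibodies (binding and if positive, neutralizing) at any time will be tabulated". SAP 4.1.2 turns this into a listing: "Listings of subjects who develop anti-darbepoetin alfa antibodies (binding and if positive, neutralizing) at any time will also be provided". SAP 5 names the output: "Listing of development of anti-darbepoetin alfa antibodies (binding and if positive, neutralizing) at any timepoint". SAP 4.1.2 expects fewer than 10 subjects, rules out summary statistics of any kind, and keeps this study's data apart from the parent study's, as Protocol 10.4 also does.

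None of these sections defines *develop* or an antibody baseline. The only baseline entry in the protocol glossary is for haemoglobin. The available SAP text begins partway through its glossary, so an entry in the missing part cannot be ruled out.

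**The concern.** The two halves of the phrase appear to pull apart. *Develop* suggests negative first and positive later. *At any timepoint* suggests that every sample counts, and one of the two scheduled samples is taken before the first dose.

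The conflicting case can arise. Subjects come from a 48-week active treatment period on the same drug (Protocol 2.3), and the first dose here "should carry forward from the last dose and frequency from the parent study" (Protocol 6.2.1.1), so the pre-dose sample is not treatment-naive. None of eligibility criteria 101 to 105 or 201 to 206 mentions antibodies.

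What would be at stake is attribution: antibodies formed under parent-study exposure could be shown as arising in this study. Where the day 1 sample is waived, the only pre-dose result belongs to the parent study, and the sentence keeping the two data sets apart might seem to forbid its use.

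**Working it through.** No figure in the plan depends on this point, so the check is to set the sampling rule against the reporting rule.

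**Step 1: where the readings differ.** Inputs: two scheduled samples (Protocol 7.3), each positive or negative, giving 2 × 2 = 4 patterns.

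| Pre-dose | End of study | Listed if any sample is positive | Listed if negative, then positive |
|---|---|---|---|
| − | − | no | no |
| − | + | yes | yes |
| + | + | yes | no |
| + | − | yes | no |

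The first reading lists 3 of 4 and the second 1 of 4. The difference, 3 − 1 = 2, is exactly the pair positive before dosing. These are possible patterns, not expected frequencies. If nobody is positive before dosing, the lists are identical.

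**Step 2: does the wording force a conflict?** No. The optional extra samples and the 3-monthly retesting give *at any time* post-dose content beyond the end-of-study visit. The phrase reads coherently as newly positive in any sample taken after treatment starts here. SAP 2.1 follows the same logic for adverse events, which count as treatment-emergent by onset within the study.

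**Step 3: the waived sample.** Protocol 7.3 itself makes the parent study's final specimen the substitute for day 1. Reading that result as the subject's pre-dose value follows the protocol. It does not pool the two studies.

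**Step 4: would a simple definition improve matters?** Take the obvious one: negative at baseline and later positive is developed; positive at baseline is pre-existing, whatever follows. The listing covers two results, so each sample has three states: none, binding only, or binding plus neutralizing. That gives 3 × 3 = 9 pre-dose/later patterns. Something new appears in three:

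- none to binding only
- none to binding plus neutralizing
- binding only to binding plus neutralizing

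The simple definition catches the first two and labels the third pre-existing. Yet under Protocol 7.3 a positive neutralizing result is the one that triggers notification of the site and, at the final visit, follow-up.

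**Step 5: size.** With at most 9 subjects, one relabelled subject would move the percentage in Protocol 10.4 by 100/9 = 11.1 points, or by 100/5 = 20 points if 5 enrolled. The SAP plans no such percentage. What remains is the label on one subject's line in a listing.

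**The case for a change.** The best case for a change is that the SAP defines AML progression, transfusion, treatment-emergent events and thrombovascular events, but gives no rule for antibodies, which carry the same carry-over problem. Two programmers could follow the text faithfully and list different subjects. In a study meant to describe longer-term safety in so few people, one wrongly attributed subject is noticeable. A definition costs a sentence and is best written before results are seen.

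Much of the factual part stands: the available text leaves the term undefined, the case can occur, and Protocol 10.4 shares the wording. The SAP also names columns for the demographic and exposure listings but none for this one, so display of sample dates is likely rather than guaranteed.

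The consequence does not stand. No estimate, test or conclusion rests on the label. The adverse-event rule works against the objection, since it shows an analyst which reading fits this plan. Site notification and retesting depend on the laboratory result, not on how the listing labels the subject. The idea that one positive sample would be reported in both studies depends on the parent study's reporting, which is not in these documents. The one-sentence remedy is also less simple than it looks, as Step 4 shows.

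**Conclusion.** No change follows. This is an undefined term in a descriptive listing that an analyst will fill sensibly, by reading *develop* as newly positive, taking the parent study's final sample as the pre-dose value where day 1 was waived, and showing binding and neutralizing results by date. The effect is confined to how between 0 and 9 subjects are labelled; the documents give no basis for a narrower range. The primary endpoint, subject incidence of treatment-emergent adverse events, is unaffected.

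The conclusion assumes that the listing shows individual sample dates and both antibody results, that the parent study's final result is available for waived subjects when the listing is run, and that the antibody output remains a listing, as SAP 4.1.2 plans, and not a percentage.
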